9.4 Adverse events that do not require reporting

Routine hospitalizations for examinations related to AN standard care will be recorded but do not require reporting.

Additionally, the following known adverse reactions associated with taking olanzapine do not require reporting:

Page 43 of 60

somnolence, weight gain, eosinophilia, elevated prolactin, cholesterol, plasma glucose or HbA1c and triglyceride levels, glucosuria, increased appetite, dizziness, akathisia, parkinsonism, leukopenia, neutropenia, dyskinesia, orthostatic hypotension, anticholinergic effects, transient asymptomatic elevations of hepatic aminotransferases, rash, asthenia, fatigue pyrexia, arthralgia, increased alkaline phosphatase, high gamma glutamyl transferase, high uric acid, high creatine phosphokinase and oedema.

9.5 Overdose

Overdoses of 500 mg olanzapine tablets at once or 30 mg daily for at least one week have been reported. Therefore, we will define 500 mg olanzapine taken at once or 30 mg overdose for at least one week as overdose [87-93]. Overdoses will be observed from reported pill counts, patient comments and plasma level measurements. In case of an overdose, study medication will stop for this participant. However, they can remain in the study until 12 months after baseline. An overdose will be fully reported and described in an SAE report form.

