7.10 Withdrawal criteria

The physician responsible for a patient can withdraw a patient from a trial or a certain aspect of the trial any time for appropriate medical reasons, be they individual adverse events or new information gained about a treatment. Trial participants also have the liberty to withdraw their consent at any time and for any reason.

A patient should stop olanzapine treatment if they show:

- If they show a QTc interval >500 ms in the ECG
- If they show rises by more than 60 msec from baseline [47] in the ECG
- Severe cardiac problems
- Serious Adverse Events (SAE) An SAE will be a withdrawal criterion if it is deemed to be related to the treatment with olanzapine by the Principal Investigator
- Serious Adverse Reaction (SAR)
- Suspected Unexpected Serious Adverse Reaction (SUSAR)

However, should a patient stop olanzapine, the patient is not necessary withdrawn from the study, every effort should be made to continue to obtain follow up data as long as the participant is willing.

The whole trial will stop in case of:

- A QTc interval >500 ms in the ECG or rises by more than 60 msec from baseline or other severe cardiac side effects in more than one patient
- Serious self-harm or suicidal behaviour in more than one patient. Serious self-harm is defined as the following:
 - Recent (within the last 12 months) self-harm with suicidal intent
 - Recent self-harm with the risk to a person's own life (e.g., drug intake, deep cutting, burning, swallowing sharp items)

• Recent self-harm which could lead, or has led, to long lasting impairment of one's health and functioning

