8 TRIAL TREATMENTS

8.1 Name and description of treatment

This trial will use the atypical antipsychotic olanzapine as the treatment. Olanzapine is a dopamine D1, D2, D4, 5-HT2, histamine- 1-, and muscarinic-receptor antagonist. In this study, olanzapine will be used as tablet or as a dispersible tablet, of 2.5, 5, 7.5 or 10 mg. Olanzapine is UK-licensed and commercially

Page 39 of 60

available on the UK market. Any brand/manufacturer of Olanzapine with a marketing authorisation in the UK can be used.

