8.7 Dosage modifications

The study will follow a slow up-titration schedule (1.25 or 2.5 mg/d increments each week for adolescents and 2.5 mg/d for adults up to a maximum of 10 mg/d for both adolescents and adults). This is the dose range we would also apply in an RCT. Olanzapine does not come as a 1.25mg/d tablet so clinicians will be instructed the halve the 2.5mg/d tablet in initial dosages.

The same down-titration increments apply after 12 months to improve patient safety. However, it will be a clinical decision outside our study whether patients continue or stop olanzapine treatment.

Page 40 of 60

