9 PHARMACOVIGILANCE

9.1 Definitions

The Medicines for Human Use (Clinical Trials) Regulations 2004 and Amended Regulations 2006 gives the following definitions:

- Adverse Event (AE): Any untoward medical occurrence in a participant to whom a medicinal product has been administered, including occurrences which are not necessarily caused by or related to that product.
- Adverse Reaction (AR): Any untoward and unintended response in a participant to an investigational medicinal product which is related to any dose administered to that participant.
- **Unexpected Adverse Reaction (UAR)**: An adverse reaction the nature and severity of which is not consistent with the information about the medicinal product in question set out in:

The summary of product characteristics (SmPC) for that product (for products with a marketing authorisation)

- Serious adverse Event (SAE), Serious Adverse Reaction (SAR) or Suspected Unexpected Serious Adverse Reaction (SUSAR): Any adverse event, adverse reaction, or unexpected adverse reaction, respectively, that:
 - results in death;
 - is life-threatening;

- required hospitalisation or prolongation of existing hospitalisation;
- results in persistent or significant disability or incapacity;
- consists of a congenital anomaly or birth defect.
- **Important Medical Events (IME) & Pregnancy:** Events that may not be immediately lifethreatening or result in death or hospitalisation but may jeopardise the participant or may require intervention to prevent one of the other outcomes listed in the definition above should also be considered serious. Although not a serious adverse event, any unplanned pregnancy will also be reported. In case of a pregnancy, study medication will stop. The pregnant study participant will be followed up until 12 months after baseline.

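### Section 9.5 counts a single intake as an overdose only from 500 mg, 50 times the daily maximum, so large non-serious intakes below that miss the automatic drug stop and the SAE form

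*Protocol*

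**What the plan says.** Section 9.5 of the protocol first gives a history: "Overdoses of 500 mg olanzapine tablets at once or 30 mg daily for at least one week have been reported". It then turns that history into a rule: "we will define 500 mg olanzapine taken at once or 30 mg overdose for at least one week as overdose". Two consequences follow. The first is "In case of an overdose, study medication will stop for this participant". The second is a full description on an SAE report form. Overdoses are to be found from pill counts, patient comments and plasma levels.

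The trial dose is far lower. Section 8.7 sets weekly up-titration as "1.25 or 2.5 mg/d increments each week for adolescents and 2.5 mg/d for adults up to a maximum of 10 mg/d", and section 8.8 repeats 10 mg as the daily maximum. Section 8.6 lets adolescents start on 1.25 mg/d and stay there. The tablet strengths are in section 8.1: "olanzapine will be used as tablet or as a dispersible tablet, of 2.5, 5, 7.5 or 10 mg".

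Other sections bear on the same event:
- 9.1 counts as serious any event that "may jeopardise the participant or may require intervention to prevent one of the other outcomes listed".
- 9.4 says that "the following known adverse reactions associated with taking olanzapine do not require reporting", and lists somnolence, dizziness and orthostatic hypotension among others.
- 7.10 lists reasons to stop olanzapine in one patient: QTc findings, severe cardiac problems, SAEs judged related, SARs and SUSARs. Overdose is not on that list. Its trial-wide stopping rule counts self-harm with a risk to the person's "own life (e.g., drug intake, deep cutting, burning, swallowing sharp items").

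On the taper, section 8.7 applies the same increments downward after 12 months and leaves continuing or stopping to a clinical decision outside the study. Section 9.2 ends active adverse event monitoring at 13 months and says that this is after down-titration. Section 12.11 gives the taper as 3-4 weeks.

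**The concern.** That an intake has been reported as an overdose does not make it the smallest intake worth calling one. Section 9.5 takes published extreme cases and uses them as a lower limit. The definition has operative force: it is what triggers the automatic stop and the SAE form, and the individual stop list in 7.10 does not supply that trigger for a large intake without serious consequences.

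The weekly limb is also loosely worded. The reported case is 30 mg daily, but the definition speaks of a 30 mg overdose, which may mean 30 mg in total or 30 mg above the prescribed dose.

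Participants are 12 to 24 years old, and section 6 notes that the product information does not recommend olanzapine below 18. Sound handling of overdose therefore matters for safety. It also matters for the secondary objective in 3.2 on the quality of adverse event reporting, and because 8.7 says that the same dose range would be used in an RCT.

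**Working it through.** **Overdose limit.** Inputs: 500 mg and 30 mg (9.5), maximum 10 mg/d (8.7, 8.8), lowest maintained dose 1.25 mg/d (8.6), tablet strengths (8.1).

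- Ratio to the daily maximum: 500 / 10 = 50. For the weekly limb: 30 / 10 = 3.
- Tablets: 500 / 10 = 50 of the largest strength, 500 / 2.5 = 200 of the smallest.
- Days of treatment: 500 / 10 = 50 at 10 mg/d, 500 / 2.5 = 200 at 2.5 mg/d, 500 / 1.25 = 400 at 1.25 mg/d.
- Just under the limit: 49 x 10 = 490 mg at once is not an overdose under 9.5.
- A full year at 1.25 mg/d: 365 x 1.25 = 456 mg, still below 500 mg.
- Weekly limb read as an excess: 30 + 1.25 = 31.25 to 30 + 10 = 40 mg/d, against 30 mg/d read as a total.

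Section 3.7 schedules dispensing at baseline, 8 weeks, 16 weeks and 6 months but gives no quantity. If one dispensing covers 8 weeks (assumption), the whole supply is 56 x 5 = 280 mg at 5 mg/d, 56 x 7.5 = 420 mg at 7.5 mg/d and 56 x 10 = 560 mg at 10 mg/d. Taking it all at once would reach the limit only at 10 mg/d. If the 6-month dispensing covers 182 days (assumption), the supply is 455 mg at 2.5 mg/d and 910 mg at 5 mg/d, so the limit would be within reach from 5 mg/d.

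**Taper (conditional on weekly steps).** One month is 365.25 / 12 / 7 = 4.35 weeks. With n = dose / step, the dose reaches zero at week n - 1 if the first cut is at month 12, or at week n if the first cut comes a week later.

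| Dose, step | n | Weeks to zero | Against 4.35 weeks |
|---|---|---|---|
| 10 mg by 2.5 mg | 4 | 3-4 | inside |
| 5 mg by 1.25 mg | 4 | 3-4 | inside |
| 6.25 mg by 1.25 mg | 5 | 4-5 | borderline (-0.35 to 0.65) |
| 7.5 mg by 1.25 mg | 6 | 5-6 | 0.65-1.65 past |
| 8.75 mg by 1.25 mg | 7 | 6-7 | 1.65-2.65 past |
| 10 mg by 1.25 mg | 8 | 7-8 | 2.65-3.65 past |

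So the 13 months in 9.2 and the 3-4 weeks in 12.11 both reproduce for 2.5 mg steps. They fail for 1.25 mg weekly steps from 7.5 mg/d upward.

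**The case against.** A reader might infer that below 500 mg the drug cannot be stopped and the intake goes unreported. The protocol does not support that.

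- The responsible physician may withdraw a patient from the trial or from part of it on medical grounds (7.10).
- Any health or safety concern goes to the responsible clinician, who also advises on whether the participant stays in the study (7.13.2).
- Noncompliance is documented and pills are counted at every follow-up visit (8.11). An independent physician reports a week-8 plasma level above the upper limit (3.3.6).
- Participants aged 12 to 15 take olanzapine accompanied by a trusted adult (3.3.1).
- The exemption in 9.4 covers listed reactions, not the excess intake itself.
- Serious cases, including important medical events, fall under 9.1, and life-endangering intake counts towards the trial-wide stop in 7.10.

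All of this stands. What is missing below 500 mg is the automatic trigger, not the ability to act. It is also fair that the remedy leaves the stop to the investigator for a non-serious intake without self-harm intent. What it adds there is that the event is named and recorded as an overdose. The ambiguity of the 30 mg limb is slight, since the sentence before it says daily, but it costs nothing to remove.

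On the taper, a reader might infer that 9.2 flatly contradicts 8.7. It does not. The weekly interval stands in the up-titration sentence, and only the increments are carried over to down-titration. The only stated taper length, in 12.11, fits 13 months. Every adolescent may use 2.5 mg steps, and stopping is decided outside the study. The conflict exists only if the weekly pace also governs the taper.

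**Conclusion.** The definition in 9.5 is set wrongly and should be changed. Applied as written, a single intake becomes an overdose at 50 times the daily maximum, and one of 490 mg without serious consequences triggers neither of the two actions that the section prescribes. The gap is confined to large, non-serious intakes, and the safeguards elsewhere reduce it without closing it. The 50-fold ratio is exact and needs no assumption; only the supply figures rest on assumed dispensing quantities.

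The taper point is secondary and conditional. If steps are weekly, adolescents reducing by 1.25 mg from 7.5 mg/d or more are still tapering when active monitoring ends, by 0.65 to 3.65 weeks. After that, 9.2 and 9.7 bring in only related or unexpected SAEs and SUSARs. The protocol does not say how many adolescents are expected at such doses, so the number affected is unknown.

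Neither point alters a feasibility endpoint or an analysis.

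**What to change.** In 9.5:
- Define overdose as any intake above 10 mg in 24 hours or any deliberate intake above the prescribed dose, and record every case.
- Require the SAE form when seriousness under 9.1 is met.
- Stop the drug when the case is serious or was taken with self-harm intent.
- Keep both present triggers for the form and the stop: 500 mg at once, and 30 mg/d worded as total daily dose for at least one week.
- In all other cases the investigator decides, so one extra tablet is only recorded.

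In 9.2, end active adverse event monitoring at the later of 13 months or completion of a taper started at month 12. Leave the 3-4 weeks in 12.11 as they are unless slower tapers are intended.

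The same amendment can correct clerical slips where the operative sections are already right. Section 2.4 gives the 2.5 mg/d start to adolescents where 8.6 gives it to adults. Section 3.3.7 calls 16 weeks the end of trial medication and omits the 6-month laboratory and pregnancy tests. Section 2.4 and the trial summary omit the adolescent 1.25 mg/d from the dose range.

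Cost: one wording amendment, some extra overdose records, and, where a slow taper is used, up to 8 - 4.35 = 3.65 more weeks of monitoring (4.65 if the taper starts at a 12-month visit held 7 days late).

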9.6 Reporting urgent safety measures

If any urgent safety measures are taken the CI will immediately and, in any event, no later than 3 days from the date the measures are taken, give written notice to the REC of the measures taken and the circumstances giving rise to those measures.

9.7 The type and duration of the follow-up of participants after adverse reactions.

Any SUSAR will be reported to the REC irrespective of how long after administration of Olanzapine the reaction has occurred until resolved.

	Who	When	How	To Whom
SAE (related or	Chief	Within 15 days of CI becoming	SAE Report form for Non-	Main REC with a copy to
unexpected)	Investigator	aware of the event	CTIMPs, available from NRES	the sponsor and DMEC
			website.	Chair
Urgent Safety	Chief	Immediately	By phone	Main REC
Measures	Investigator			
		Within 3 days	Notice in writing setting out	Main REC with a copy sent
			reasons for the urgent safety	to the sponsor. The MREC
			measures and the plan for future	will acknowledge this
			action.	within 30 days of receipt.
Progress Reports	Chief	Annually (starting 12 months	Annual Progress Report Form	Main REC with a copy to
	Investigator	after the date of favourable	(non-CTIMPs) available from the	the sponsor
		opinion)	NRES website	
Declaration of the	Chief	Within 90 days (conclusion)	End of Study Declaration form	Main REC with a copy to
conclusion or early	Investigator	Within 15 days (early	available from the NRES website	the sponsor
termination of the		termination)		
study		The end of study should be		
		defined in the protocol		

Table of reporting responsibilities

10 STATISTICS AND DATA ANALYSIS

10.1 Sample size calculation

According to the guidance given by the NIHR Research Design Service London, https://www.rds-london.nihr.ac.uk/resources/justify-sample-size-for-a-feasibility-study/, a reasonable sample size can be

Page 44 of 60

between 30 and more than 50 [94,95]. According to the call, our proposed feasibility study should cover: Willingness to accept and adhere to the intervention; a demonstration that adherence can be measured; estimated numbers of young people potentially eligible for recruitment; key parameters of a potential future trial to include a justification of the choice and timing of an appropriate primary outcome measure. Given the variety of parameters, a figure at the upper end of the recommended range seemed plausible to us. We also have also carried out a sample size calculation for this feasibility study based on estimating the feasibility parameter "rate of adherence": Assuming that 70% of patients took olanzapine for at least 16 weeks, a sample size of 55 patients can estimate a 95% confidence interval for this parameter with 12.2% margin of error (i.e., expected CI from 57.8% to 82.2%; for a more extreme attrition rate of 50% the margin of error increases to 13.3%).

10.2 Planned recruitment rate

This is a feasibility study to test recruitment. In the months 2 to 7 of the project, we are aiming to recruit 55 patients

10.3 Statistical analysis plan

The statistical analysis plan will include a mixed-methods analysis utilizing summary statistics and qualitative analysis of the feasibility outcomes.

10.3.1 Summary of baseline data and flow of patients

Page 46 of 60

10.3.2 Primary outcome analysis

The main outcome is feasibility.

Summary statistics will be presented on the following for feasibility and may include estimation of confidence intervals:

- Patients approached, screened, and included in the study
- Adherence, completed physical assessments (including BMI measurement) and questionnaires

10.3.3 Secondary outcome analysis

Descriptives (including completeness) will be reported for the following measures: demographics, alcohol, smoking and substance use, body weight and BMI, ED psychopathology, general psychopathology, health economic and quality of life assessments, laboratory parameters (kidney function, liver function, blood count, plasma glucose, HbA1c and lipid profile), drug adherence and safety.

The safety outcomes will include:

- Summary statistics on "concerning" and "alerting" laboratory and ECG parameters according to [47]
- Descriptives of other safety parameters
- Summary of reported AEs and SAEs

10.3.4 Exploratory analyses

- We will also perform exploratory analyses looking at change over time in measures listed in Section 10.3.3 to inform a future definitive study design. Such analyses will use appropriate longitudinal modelling approaches; further details will be covered in the Statistical Analysis plan.
- Elements that constitute TAU will be described.
- Patient experience of recruitment and treatment, acceptability and reasons for adherence and nonadherence will be ascertained in qualitative interviews which will be performed, transcribed and analysed.

10.3.5 Qualitative analysis

We will conduct individual qualitative interviews in a subgroup (estimated 30 individuals) of young people with AN who either agree or decline to participate in the OPEN feasibility study. There are two main aims of the qualitative interviews: deciphering the barriers of inclusion for the study and also follow up interviews with questions concerning reflections of their participation. Interviews will examine the decision-making process and the perceived risks and advantages of taking olanzapine within the study. At the point of recruitment, participants will be asked why they agreed or refused to take part in the study. We will also ask for their permission to share their details for subsequent publications. Those who are

Page 47 of 60

recruited to OPEN will be interviewed after the 16-week assessment point about their perceptions prior to participation and their subsequent experiences of olanzapine treatment and the study design, including the perceived burden of completing outcome measures and attitudes towards randomisation in a future clinical trial. We will interview people who have adhered to olanzapine as well as people who have dropped out. The qualitative researcher will aim for 'empathic neutrality', posing open and non-leading questions that invite participants to recount their experiences of the study and treatment from their perspective.

Purposive sampling will be conducted based on gender, age, recruitment source, BMI at baseline and adherence to explore a range of perspectives. A further 10-15 interviews with health care professionals across settings will explore the perceived challenges and facilitators to recruitment and retention. Qualitative data will be analysed using the Framework Approach [85] to facilitate analysis within and between individual cases and groups of participants. The thematic framework will draw on a priori issues around the acceptability of the intervention and design study, but also be responsive to emergent themes.

All qualitative interviews will be carried out by the UK qualitative researcher (TBA2).

Two PhD student studying at King's College London under the supervision of [name] and [name], will assist [name] will the qualitative data collection and analysis.

10.4 Subgroup analysesWe do not plan any subgroup analyses.

10.5 Adjusted analysis We do not plan any adjusted analyses.

10.6 Interim analysis and criteria for the premature termination of the trial We do not plan any interim analyses.

10.7 Procedure(s) to account for missing or spurious data

The trial manager will monitor the integrity and completeness of the data weekly and approach clinical services for missing information. Trial statisticians will also monitor integrity and completeness of the data periodically and report discrepancies to the trial manager, at least prior to every DMC meeting.

We do not plan to impute or otherwise handle missing data in the analyses. Instead, missing data in this feasibility study will inform the potential application for a full RCT about risks to data completeness and integrity.

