3.1 Primary objective

The primary objective of this feasibility study is to assess the **feasibility** of carrying out such a trial to inform a future definitive RCT. This includes

- To assess the proportion of patients in different settings (adolescent/adult, inpatient/daycare/ outpatient) who
 - agree to take olanzapine (un-blinded, real-life conditions)
 - adhere to olanzapine
 - complete all study assessments and questionnaires at the five assessment points.

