3.3.6. Drug adherence measures

Olanzapine plasma level: We will perform therapeutic drug monitoring and measure olanzapine levels at week 8 after the start of olanzapine treatment. [70]. An independent physician will have immediate access to olanzapine levels, and feedback to the study team if the level exceeds the upper normal limit. Pill count: We will use the pill count as an indirect measure of adherence. Thus, the number of dosage units that have been taken/not taken will be counted. We are, however, aware that the removal of a dosage unit does not mean that the medication has been taken, that it does not characterize the adherence pattern, and that it is unable to identify causes of adherence or non-adherence. Therefore, we will use pill count in addition to the olanzapine plasma level [71].

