3.4 Primary endpoint/outcome

Primary objective: feasibility

Primary endpoints: Assessing the proportion of patients in different settings, examining different methods to measure adherence (questionnaire, pill count, olanzapine plasma level). Important measurement time points are the baseline and 12 months after baseline.

Summary statistics will be presented on the following for feasibility and may include estimation of confidence intervals:

Patients approached, screened and included in the study

Adherence, completed physical assessments (including BMI measurement) and questionnaires

Willingness to take part in an RCT

Elements that constitute TAU

Summary statistics on psychopathology, general psychopathology and quality of life assessments and change in BMI will also be reported.

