7.2 Consent

The CI will have overall responsibility for the conduct of research. The CI will ensure that any person delegated responsibility to participate in the informed consent process is duly authorised, trained and competent to participate according to the ethically approved protocol and principles of Good Clinical Practice (GCP) and Declaration of Helsinki.

Informed consent will be obtained prior to the participant undergoing the baseline assessments.

Written consent will be taken by the members of the research team at each site. The Patient Information and Consent forms will be given to the participants and ample time will be given for the participants to review and complete the forms and for any questions to be answered. One copy of the signed consent forms will be given to the patient, one copy will be kept in the patient medical notes and one copy will be filed in the Site File.

The right of a participant to refuse participation without giving reasons must be respected, and the participant will remain free to withdraw at any time from the trial without giving reasons and without prejudicing his/her further treatment and will be provided with a contact point where he/she may obtain further information about the trial. This contact point will be the researcher and the CI.

Data and samples collected up to the point of withdrawal will only be used after withdrawal if the participant has consented for this. This is explained in the information sheet and specified in the consent form. Patients under 16 years old will be required to assent to take part in the trial and a consent from a parent/legal guardian will be obtained. Participants who turn 16 years old during the study will be required to consent, and it is the responsibility of the PI to ensure this is done in a timely manner. The PI will take responsibility for ensuring that all participants are protected and participate voluntarily in an environment free from coercion or undue influence.

We will only include patients who can read and write in English.

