8.9 Concomitant medication

Caution is advised for the drugs listed in the previous section as concomitant medication. However, there is no contraindication for the monotherapy with olanzapine. Additionally, blood concentration of olanzapine will be monitored throughout the study. Contraindications according to the BNF apply to elderly patients who will not be included in this trial and to patients who receive olanzapine as intramuscular application which is not envisaged in this trial either.

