8.11 Assessment of compliance with treatment

Compliance will be assessed by

- Measurement of the olanzapine plasma level 8 weeks after baseline
- Pill count, self-reported by the patient at 8 weeks, 16 weeks, 6 months, and 12 months after baseline.

Noncompliance to the protocol trial procedures will be documented by the investigator. Noncompliance will not lead to withdrawal from the trial. This is a feasibility study which will find out the rate of compliance or noncompliance as well as the rate of participation in assessments and assessment completion.

Compliance and non-compliance are part of the qualitative research aspect of this feasibility study.

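### Primary adherence proportion: no denominator is fixed and handling of missing data is ruled out, although the trial is sized on all 55; the by-setting objective has no matching analysis or precision statement

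*Protocol*

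**What the plan says.** **Missing data.** Section 10.7: "We do not plan to impute or otherwise handle missing data in the analyses". It adds that missingness will instead inform a later RCT application, and that the trial manager checks completeness weekly. Section 7.2 limits what may be used from withdrawers: "Data and samples collected up to the point of withdrawal will only be used after withdrawal if the participant has consented for this".

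**Sizing.** Section 10.1 sizes the trial on adherence: "Assuming that 70% of patients took olanzapine for at least 16 weeks", N = 55, margin 12.2 points (57.8% to 82.2%). The margin is 13.3 points for an alternative of 50%, which it calls an attrition rate.

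**Objective and analysis.** Section 3.1: "To assess the proportion of patients in different settings" (adolescent or adult; inpatient, day care or outpatient) who agree to take, adhere to and complete. Section 3.4 repeats the by-setting wording for the primary endpoint and says "Important measurement time points are the baseline and 12 months after baseline". Section 10.3.2 plans summary statistics with optional confidence intervals. It names no setting, denominator or adherence time point. Section 10.4 plans no subgroup analyses.

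**Measurement.** Section 3.3.6 plans to "measure olanzapine levels at week 8 after the start of olanzapine treatment", and 8.11 agrees, but 8.9 says "blood concentration of olanzapine will be monitored throughout the study". Section 3.3.6 has dosage units counted, and the schedule in 3.7 assigns the count to the researcher and clinical team. Section 8.11 has "Pill count, self-reported by the patient at 8 weeks, 16 weeks, 6 months, and 12 months after baseline". Sections 3.2 and 3.4 list a questionnaire among the adherence measures. None appears under adherence in 3.3.6, 3.7, 7.7 or 8.11.

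**The concern.** Adherence is part of the primary objective, the only parameter on which the trial was sized, and a main input to any later RCT. Patients who leave the study are the most likely to lack a 16-week pill count, and leaving plausibly goes with having stopped the drug. A rule that excludes any handling of missing data permits a figure based on those who stayed. That is a different quantity from the one in 10.1, and it could make a regimen look more workable than it is.

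The primary objective also asks for proportions by setting, while the analysis and precision sections address one pooled group. A reader could take the 12.2-point margin to apply to setting-specific figures, where it does not.

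**Working it through.** **1. The plan's own figure.** Inputs from 10.1: p = 0.70 and 0.50, n = 55, 95% two-sided. Half-width = 1.96 × √[p(1−p)/n].

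- With n = 55: 12.11 points at 70%, 13.21 at 50%.
- With n − 1 = 54 in the denominator: 12.22 and 13.34. These match the stated 12.2 and 13.3.

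The stated margin is therefore correct for 55 patients, pooled, with no missing adherence data. With 40 observed at 70%, it would be 1.96 × √(0.21/40) = 14.2 points before any bias.

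**2. What missing data can do to the estimate.** The only dropout figure in the protocol is 28% (section 1.3, pooled from other studies). Using it as the share without 16-week data is an assumption: 0.28 × 55 ≈ 15 missing, 40 observed. Suppose 28 of the 40 adhere (70%).

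| Treatment of the 15 missing | Proportion |
|---|---|
| Left out | 28/40 = 70.0% |
| All non-adherent | 28/55 = 50.9% |
| All adherent | (28 + 15)/55 = 43/55 = 78.2% |

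The lower bound lies below the planned 57.8%.

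**3. The reverse direction.** Suppose 38 of 55 (69.1%) truly adhere and every missing patient is non-adherent. The observed-only figure is then:

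- 6 missing: 38/49 = 77.6%
- 11 missing: 38/44 = 86.4%
- 15 missing: 38/40 = 95.0%

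This is the extreme case. More generally, with 70% true adherence (38.5 of 55), 28% missing (15.4) and a fraction f of the missing adherent, the observed-only figure is (38.5 − 15.4f)/39.6:

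| f | Observed-only |
|---|---|
| 0 | 97.2% |
| 0.25 | 87.5% |
| 0.5 | 77.8% |
| 0.7 | 70.0% (no bias) |

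Above f = 0.7 the bias turns downward.

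**4. Precision by setting.** The protocol gives no split, so equal splits are assumed. Half-widths at 70%:

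- Two age groups (27.5 each): 1.96 × √(0.21/27.5) = 17.1 points
- Three care settings (18.3 each): 1.96 × √(0.21/18.33) = 21.0 points

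Exact 95% intervals at nearby whole numbers: 20/28 gives 51.3% to 86.8%; 13/18 gives 46.5% to 90.3%.

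**5. Measurement at 16 weeks.** The plasma level is scheduled at week 8 only and the questionnaire is not scheduled. The pill count is therefore the only listed adherence measure at 16 weeks, and the sections differ on who provides it.

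**The case against.** A reader might infer that the plan overstates adherence. The protocol does not establish that. No section restricts the denominator to patients with data, and 10.1 points towards all 55. Patients who stop olanzapine are not necessarily withdrawn and are followed if willing (7.10), and non-compliance is not a reason for withdrawal (8.11), so a known stopper is an observed non-adherer. Withdrawal information is collected as CONSORT data, and 10.7 has clinical services approached for missing information. The 28% is a trial-dropout rate from other studies, attributed mainly to personal or study-related reasons; it is not a rate of missing adherence data here. All this stands, and it makes the upward bias conditional.

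A reader might also infer that the by-setting objective cannot be answered. That goes too far. Section 10.4 can be read as excluding formal comparisons only, descriptive proportions remain possible, and wide intervals are ordinary in a feasibility study of 55.

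The SAP, which is not at hand, may define the denominator, and missingness is itself an outcome of this study. But 10.7 is a stated rule, not a silence: its wording excludes other handling as well as imputation, so counting missing as non-adherent would contradict it. The only SAP deferral within section 10.3 concerns the exploratory longitudinal models (10.3.4).

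On time points, 16 weeks in 10.1 and 12 months in 3.4 are not mutually exclusive. The weakness is that 10.3.2 ties the primary figure to neither.

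**Conclusion.** The point holds as an inconsistency between the sizing and the analysis rule, with a conditional bias. Section 10.1 implies a proportion of all 55 with attrition counted against adherence; this is an inference from its use of N = 55 and its attrition label. Section 10.7 permits a proportion of those observed. Under the assumed 28% missing, these readings differ by 19 points (70.0% against 50.9%), more than the 12.2-point margin. The direction is upward if patients with missing data adhere less than the rest; it disappears if they adhere equally and reverses if they adhere more.

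The by-setting mismatch between 3.1 and 3.4 on one side and 10.1, 10.3.2 and 10.4 on the other is real but reconcilable. Margins of about 17 and 21 points rest on equal splits and 70% adherence. The plasma-timing and questionnaire discrepancies can be read directly from the text. The pill-count wording is milder, since a count and a self-report could coexist, but it needs clarifying.

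**What to change.** - **10.3.2 and 10.7:** define primary adherence as patients still taking olanzapine at 16 weeks divided by all enrolled, with missing counted as non-adherent. Give observed-only and best-case (missing counted as adherent) figures as bounds, and 12-month persistence as a second figure. Amend the sentence in 10.7 so that it does not forbid this.
- **Withdrawers:** keep them in the denominator within the consent terms of 7.2. Where those terms bar use of a participant's adherence data, the outcome is missing and is handled as above.
- **10.4:** state that the primary proportions are reported descriptively by age group and by care setting, with exact confidence intervals and no formal comparison.
- **10.1:** say that the 12.2-point margin is for the pooled sample only.
- **Reconcile:** plasma-level timing (3.3.6 and 8.11 against 8.9); who counts pills (3.3.6 and the schedule against 8.11); and the adherence questionnaire named in 3.2 and 3.4, which should be either scheduled or deleted.

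The cost is wording only. The downside is a lower headline adherence figure and wider stated margins by setting. Counting missing as non-adherent is a conservative convention, which is why the two bounds should appear beside it.
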